### **6.3.2 Medical History other than CAD**

A summary table of medical history on the medical history eCRF page will be shown.

Medical history will be coded using the latest available version of the Medical Dictionary for Regulatory Activities (MedDRA) coding dictionary. Summary tables of the number and percentage of patients with medical history by system organ class (SOC) and preferred term (PT) will be produced for patients in the safety set. Medical history will be sorted in descending order of frequency in the pegcetacoplan group. For the summary tables, a patient may appear more than once if they have more than 1 medical history finding coded under different SOC terms or more than 1 medical history finding with a different PT under the same SOC term. However, the patient will be counted only once in each SOC.

A patient medical history listing with coded SOC and PT along with verbatim eCRF term will also be provided.

### **6.3.3 Alcohol Consumption and Smoking History**

A summary table will be shown to present data from the alcohol consumption and smoking history eCRF page.

### **6.3.4 Bone Marrow Biopsy History**

A summary table will be shown to present data from the bone marrow biopsy eCRF page including MYD88 mutation test result and presented in a listing.

## **6.4 PRIOR AND CONCOMITANT MEDICATIONS AND PROCEDURES**

### **6.4.1 PRIOR AND CONCOMITANT MEDICATIONS**

Separate summary tables will be provided for prior and concomitant medications in the safety set, presenting the number and percentage of patients by each treatment group.

All prior and concomitant medications will be coded using the latest version of World Health Organization drug dictionary (WHO Drug Global).

Medications will be presented by ATC level 2 (therapeutic main group) and ATC level 5 (standardized medication name) with numbers and percentages by treatment group and overall. A patient who takes more than one medication will be counted only once if these medications belong to the same extended ATC classification.

In the summary tables, prior medications and concomitant medications will be presented by decreasing frequency of patients overall within each ATC level 2 class and then similarly by decreasing frequency of patients overall within each ATC level 5 class. In cases of ATC level 2 classes or ATC level 5 classes with equal frequencies, medications will be sorted alphabetically.

Prior medications will be defined as those medications administered within 12 weeks prior to the time of informed consent. Concomitant medications will be defined as those medications taken following the time of informed consent.

Hence medications started before informed consent but continuing after will be considered as both prior and concomitant medications. The listing of medications will identify prior and concomitant medications.

For the purposes of identifying prohibited medications, medical judgment will be involved in interpreting partial dates, if any.

All prior and concomitant medications will be listed.

#### **6.4.2 CONCOMITANT PROCEDURES**

Prior and concomitant procedures will be presented in a summary table with numbers and percentages of patients by procedure.

Prior procedures will be defined as those procedures performed within 12 weeks prior to the time of informed consent. Concomitant procedures will be defined as those procedures performed following the time of informed consent.

All prior and concomitant procedures will be listed.

#### **6.5 PROPHYLATIC ANTIBIOTICS, PRIOR VACCINES AND PRIOR CAD THERAPY**

Prophylactic antibiotics taken after first dose of study drug as captured on the prophylactic eCRF page will be summarized in a table and listed.

Prior vaccines, as recorded on the prior vaccination eCRF page, will be summarized in a table and listed.

Prior CAD therapy, as recorded on the prior CAD therapy eCRF page, will be summarized in a table and listed.

#### **6.6 PROTOCOL DEVIATIONS**

A summary table of protocol deviations will be provided and a listing of all protocol deviations by patient will be provided.

Protocol deviations that may significantly impact the quality (i.e., completeness, accuracy, and reliability) or integrity of key trial data will lead to exclusion of the patient from the PP set. Final decisions about protocol deviations that may lead to exclusion from the PP set will be made prior to database lock at a blinded data review meeting.

Examples of such protocol deviations include but is not limited to:

- Non-compliance with study drug (less than 80 % of planned infusions)
- Not fulfilling the CAD diagnostic criteria at study entry
- Use of medication that can influence the efficacy endpoints (for example medications used outside of the definition of permitted concomitant medication as in the protocol)
  - Note: Prohibited medication as defined in the protocol is not to be considered a protocol deviation to exclude a patient from the PP, these are handled as intercurrent events (ICEs)

## 6.7 PHYSICAL EXAMINATIONS

Physical examinations will be described in a data listing.

## 6.8 TREATMENT COMPLIANCE AND EXPOSURE

Definitions of exposure variables are provided below.

Variables	Definitions
Duration of treatment (days)	Date of last dose of treatment – date of first dose of treatment +1
Study treatment compliance (%)	$100 * (\text{total number of infusions}) / (\text{total number of infusions planned to be taken})$ . The total number of infusions planned to be taken will be calculated as 2 times the number of weeks a patient is on treatment. It is noted that the number of weeks a patient is on treatment will be estimated as (date of EOT visit – date of first treatment +1)/7 rounded up to next integer.

A compliance and exposure summary table will be presented that summarizes duration of treatment, study treatment compliance, and number of infusions received for patients in the safety set.

The number and percentage of patients who had a percentage of drug compliance range by increment of 10 % ( $\geq 80\%$  to  $90\%$  and  $\geq 90\%$  to  $\leq 100\%$ ) will be presented in a table by treatment group.

The following parameters will be calculated and presented using the safety set:

- Total dose administered (mg)
- Duration of treatment (days)
- Number and percentage of patients who received infusions
  - Number and percentage of patients with all infusions completed

- Number and percentage of patients with any infusion interrupted
- Total number of infusions
- Number and percentage of infusions completed
- Number and percentage of infusions interrupted

Duration of treatment, study treatment compliance, and number of infusions will also be presented in a listing.

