6.1.2 Double-blind treatment period (24 weeks): Part A

A total of 57 patients who meet all of the inclusion criteria and none of the exclusion criteria will be randomized in a 2:1 ratio to receive either pegcetacoplan or placebo.

Patients randomized into the study will receive IMP (pegcetacoplan or placebo) twice weekly for 24 weeks.

All standard-of-care medications can be continued, with the exception of protocol-defined prohibited medications (see Section 6.4.10.2).

During the double-blind treatment period, patients will receive a blood transfusion if their Hb level is ever shown to be < 7.0 g/dL. During this study period, transfusions will be considered, at the investigator's discretion, in symptomatic patients with Hb levels ≥ 7.0 and < 9.0 g/dL.

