6.4.5 Selection and timing of doses for each patient

Patients will self-administer s.c. IMP, after receiving appropriate training by research personnel. IMP will be dosed at the clinical site on Day 1. On dosing days that coincide with clinic visits, doses will be administered at the clinic visit.

Patients will be instructed to self-administer their IMP only as prescribed and to contact the investigator immediately for guidance in the event of any missed doses.

Dosing diaries will be used for study treatment and are to be completed for each dose administered at the clinic or at home. Patients should not deviate from the IMP dosing schedule: Day 1 and Day 4 of each treatment week (e.g., Monday/Thursday/Monday/Thursday).

The preferred site of infusion will be the abdomen. If administration into the abdomen is not feasible, alternative appropriate sites are acceptable (see the Pump Instructions for Use document for more details).

The typical s.c. infusion time for pegcetacoplan is approximately 30 minutes if using 2 sites, or approximately 60 minutes if using 1 site.

During initial qualification, the research nurse or other appropriately qualified and trained research personnel will administer the s.c. infusions (as needed) and will qualify and supervise the self-administration or caregiver administration. These qualified research personnel will be made available for a minimum of 2 doses to ensure the patient has been qualified to conduct self-administration; the duration can be shortened if qualification happens sooner. During qualification, the patient or caregiver must demonstrate to the research personnel their ability to safely and effectively administer the IMP using the infusion pump. Following self-administration or caregiver administration qualification, patients or caregivers may self-administer the s.c. infusions without supervision. Once qualified, the patient or caregiver will continue to administer infusions at the clinic on those days when a clinic visit occurs and at an off-site location convenient to the patient on all other days. Self-administration or caregiver administration conducted at the clinic will be supervised to ensure that the patient or caregiver continues to remain compliant with the administration guidelines.

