	Week 16	113	100 – 127	28
	Week 20	141	128 – 155	28
	Week 24	169	156 - 197	42
Open label treatment period (Part B)	Week 32	225	198 - 253	84
	Week 40	281	254 - 309	84
	Week 48	337	310 - 365	84
Open label maintenance period (Part C)	Week 56	393	366 - 421	84
	Week 64	449	422 - 477	84
	Week 72	505	478 - 533	84
	Week 80	561	534 - 589	84
	Week 88	617	590 - 645	84
EOT	Week 96	673	N/A	N/A
EOS	Week 104	729	N/A	N/A
	* Manually adjusted to allow +/- 7 at Week 4 visit as allowed in protocol			

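### The SAP 6.8 compliance formula counts up to two infusions that were not due when the EOT visit is on its target day, more if the visit lags, and sets no Part A end date

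*SAP*

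**What the plan says.** SAP 6.8 defines compliance as 100 times infusions received over infusions planned. Planned infusions are "2 times the number of weeks a patient is on treatment", and the weeks are estimated as the bracketed difference "date of EOT visit – date of first treatment +1)/7 rounded up to next integer". In the same table, duration of treatment ends at the last dose, not at the EOT visit. The section then calls for a frequency table "by increment of 10" percentage points, naming two bands: from 80% to 90%, and from 90% to 100%.

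The dosing schedule is in the protocol. Section 6.1.2 states: "Patients randomized into the study will receive IMP (pegcetacoplan or placebo) twice weekly for 24 weeks". Section 6.4.5 fixes the dosing days as "Day 1 and Day 4 of each treatment week".

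SAP 5.2.3 gives Week 24 a target day of 169 and EOT (Week 96) a target day of 673. It also treats the Week 24 visit as both the end of Part A and the start of Part B dosing. Protocol 6.1.5 places the EOT visit after Part C or at early discontinuation.

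SAP 6.6 lists "Non-compliance with study drug (less than 80 % of planned infusions" as one example of a deviation that can remove a patient from the per-protocol set. SAP 1.1 drops the per-protocol analyses after the early stop of enrolment, but keeps the safety summaries as planned.

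**The concern.** A compliance percentage should compare the doses taken with the doses that were due. This denominator does something else in three respects.

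- From Week 1 on, each target visit day is one day past a whole number of weeks. Adding one day and then rounding up turns that single day into a full extra week.
- The clock runs to the EOT visit, so days after treatment has ended count as days on which infusions were planned.
- A patient who continues into Part B has no EOT visit at Week 24. The SAP reports Part A on its own (sections 7.6 and 8), yet 6.8 does not say which date closes the Part A denominator.

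At stake is the accuracy of the compliance table and the per-patient listing, both still planned. A reader of the report could take an artefact of the formula for missed doses. Early stoppers are exposed most. With enrolment ended and treatment allowed only until 10 July 2024 (SAP 1.1), EOT visits before Week 96 are likely.

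**Working it through.** **Inputs**
- Doses on Days 1, 4, 8, 11 and so on (Protocol 6.4.5).
- 24 weeks of double-blind treatment, twice weekly (Protocol 6.1.2).
- Week 24 on Day 169 and EOT on Day 673 (SAP 5.2.3).
- Weeks = (EOT visit date − first dose date + 1)/7, rounded up; planned = 2 × weeks (SAP 6.8). With first dose on Day 1, the bracket equals the study day of the visit.

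**The plan's own figure.** The documents state no compliance percentage. They do fix the Part A dose count: 24 × 2 = 48, the last on Day 165 (7 × 23 + 4). The formula does not return 48 at the Week 24 target day.

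**Formula against schedule, for a patient who misses nothing**

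| End date | Day/7 | Weeks | Planned | Due before that day | Shown as |
|---|---|---|---|---|---|
| Day 168 | 24.00 | 24 | 48 | 48 | 100% |
| Day 169 (Week 24) | 24.14 | 25 | 50 | 48 | 96.0% |
| Day 175 | 25.00 | 25 | 50 | 50 | 100% |
| Day 176 | 25.14 | 26 | 52 | 50 | 96.2% |
| Day 673 (EOT target) | 96.14 | 97 | 194 | 192 | 99.0% |

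Day 673 is the formula's own anchor. Day 169 applies only if the EOT visit falls on that day, or if Week 24 is substituted as the Part A end. If a dose given on the visit day is counted, the results are 49/50 = 98.0% and 193/194 = 99.5%.

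**Effect at the cut points**
- Day 169: 39 infusions are 39/48 = 81.3% but show as 39/50 = 78.0%. This is the only count that crosses 80%, since 40/50 = 80.0% is not below it. At the 90% cut, 44 infusions are 44/48 = 91.7% but show as 44/50 = 88.0%.
- Day 673: 154 infusions are 154/192 = 80.2% but show as 154/194 = 79.4%. 155 infusions are 80.7% but show as 79.9%.

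**Early stoppers.** I found no maximum interval between last dose and the EOT visit in the documents, so the lag below is an assumption, shown over a range. Take a patient with the last dose on Day 57 and all 17 doses taken (8 × 2 + 1):
- EOT Day 58: 58/7 = 8.29, so 9 weeks and 18 planned; 17/18 = 94%.
- EOT Day 64: 64/7 = 9.14, so 10 weeks and 20 planned; 17/20 = 85%.
- EOT Day 71: 71/7 = 10.14, so 11 weeks and 22 planned; 17/22 = 77%.

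True compliance is 17/17 = 100% in every row.

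**The case against.** The strongest reply is that the formula is tied to the EOT visit, not to Week 24. A reader might infer that every fully compliant Part A patient will show 96%. The text does not support that: a patient who goes on to Part B has no EOT visit on Day 169, and a Week 96 completer shows 99.0%. This stands, and the 96.0% is conditional for that reason. It also exposes the missing Part A end date.

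Nor is the understatement universal. For a patient dosed up to the EOT visit, the excess is two infusions on Day 7k+1, one on Days 7k+2 to 7k+4, and none on Days 7k+5 to 7k+7, leaving out a dose on the visit day. A late visit does not by itself make matters worse: at Day 176 one might divide 48 by 52 and get 92%, but a patient who stays on schedule has had 50 doses by then, giving 96.2%.

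A reader might also infer that the formula drives the 80% deviation flag and so changes an analysis set. SAP 6.6 does not cite 6.8. It gives the threshold as an example, to be settled at a blinded data review meeting, and the per-protocol analyses it served were dropped. That inference fails.

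On the bands, the wording about increments may imply more categories than the two named. The continuous summary and the listing would still show values outside 80% to 100%. This softens the point about the bands, though the SAP's own 80% threshold has no explicit category beneath it, and 90% is not clearly assigned to one band.

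The SAP calls the week count an estimate. That does not excuse it when the exact count follows from a fixed dosing schedule.

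**Conclusion.** The rule is wrong as written, and the matter is minor. With an EOT visit on its target day, planned infusions are overstated by two: 194 against 192 at Week 96, and 50 against 48 where Day 169 is the end date. That lowers full compliance to 99.0% and 96.0% respectively. The larger distortion is for early stoppers, where the size depends on an assumed visit lag: 94%, 85% or 77% for a fully adherent patient seen 1, 7 or 14 days after a last dose on Day 57. The Part A denominator is undefined for patients who continue.

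These figures rest on on-schedule dosing and on excluding a dose given on the visit day. The consequence stops at the descriptive compliance table and listing for the safety set. A reader might suspect an effect on efficacy conclusions, but those are drawn from the ITT set, and no endpoint or test uses this percentage.

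**What to change.** Replace the week-based denominator in SAP 6.8 with a count of the scheduled Day 1 and Day 4 doses due from first dose to the end of each study part, or to the treatment discontinuation date if earlier. State that Part A runs up to, but does not include, the first Part B dose, which gives 48 for an on-schedule completer. Count received infusions over the same interval.

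Removing the added day alone is not enough. It restores 24 weeks at Day 169 (168/7 = 24), but leaves the early-stopper lag and the missing Part A end date untouched.

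Tabulate the bands as below 80%, 80% to below 90%, 90% to 100%, and above 100%.

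The cost is a wording change and one derivation. Protocol 6.3.3.1 already has the last-dose and treatment-withdrawal dates recorded in the eCRF, so no new data are needed.

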## 7 STUDY ENDPOINT ANALYSES

### 7.1 PRIMARY ENDPOINT ANALYSIS

The primary endpoint is response to treatment at Week 24, with response defined as:

- An increase in Hb of  $\geq 1.5$  g/dL from Baseline or Hb normalization at Week 16; AND
- Maintenance of this effect from Week 16 to Week 24; AND
- The absence of PRBC transfusions (between Week 5 and Week 24)

Note: Hb normalization is defined as within normal range ( $\leq$  the ULN and  $\geq$  the LLN, as set by the testing laboratory reference ranges. Hb will be assessed locally.

Maintenance of effect is defined as the average change from Baseline in Hb of Week 16, Week 20 and Week 24  $\geq 1.5$  g/dL or the average Hb at these time points within normal range.

If response can't be evaluated (Hb at Week 16 and/or at Week 24 is missing) the patient will be considered to be a non-responder. If data at Week 20 is missing, the average of Week 16 and Week 24 will be used to calculate maintenance of effect.

The absence of PRBC transfusions will be assessed from Day 29 and until the end of the double-blind period (Week 24 or early withdrawal).

The primary analysis will be conducted on the ITT.

The estimand will be a composite where patients having an ICE will be considered as non-responders. The ICES of interest are:

- Withdrawal from treatment or lost to follow-up before end of the double-blind period
- Use of prohibited medications (rituximab alone or in combination, any other complement inhibitor, any other investigational drug and plasma exchange. ).

The number and percentage of patients who respond will be tabulated by treatment group and compared between treatment groups using an exact Cochran-Mantel-Haenszel (CMH) test stratified for the criterion used for stratification of randomization ( $\geq 1/0$  transfusions during the 6-month period prior to randomization). The odds ratio of being a responder for the pegcetacoplan treatment group versus the placebo group and associated exact 95% CI and p-

value will be provided. The responder rate, difference between treatment groups and 95% CI will also be reported.

As supportive analyses, the above will be repeated using the PP set and mITT set.

### 7.1.1 Subgroup analyses

Subgroup analyses on the primary endpoint will be conducted for:

- The strata with  $\geq 1 / 0$  transfusions during the 6 months prior to randomization. Fisher's exact test will be used for this subgroup analysis.
- The subgroups of patients previously treated with rituximab / rituximab-naïve patients.

Baseline will be taken as the last measurement prior to the first dose of IMP. All efficacy data will be listed.

## 7.2 KEY SECONDARY EFFICACY ENDPOINT ANALYSES

The key secondary efficacy analyses in this section will be analyzed based on the ITT.

To preserve the Type 1 error, a fixed-sequence testing strategy will be used; hence, statistical significance with the first key secondary endpoint will only be concluded if statistical significance is achieved with the primary analysis of the primary endpoint. The ordering of the key secondary endpoints in this testing strategy will be in the following order:

- Change from Baseline to Week 24 in Hb level
- Transfusion avoidance (Yes/No) from Week 5 to Week 24
- Change from Baseline to Week 24 in the FACT-An score

The hierarchical testing will be applied to the primary and key secondary endpoints, no further multiplicity control will be applied.

### 7.2.1 Subgroup analyses

For all key secondary endpoints, subgroup analyses will be presented for the following subgroups:

- The strata with  $\geq 1 / 0$  transfusions during the 6 months prior to randomization.
- The subgroups of patients previously treated with rituximab / rituximab-naïve patients.

For continuous endpoints the same MMRM model will be used for analysis except for omitting strata from the model. For transfusion avoidance Fisher's exact test will be used.

### 7.2.2 Change from Baseline to Week 24 in Hb level

The ICES for the change from Baseline to Week 24 in Hb analysis, and their associated strategies to handle them, will be as follows:

- Withdrawal from treatment or lost to follow-up before end of the double-blind period (all measurements after withdrawal or lost to follow up will be set to missing);
- Use of prohibited medications (all measurements after prohibited medication start date will be set to missing)

- Transfusion from week 5 to week 24 (all measurements after transfusion will be set to missing)

The change from Baseline to Week 24 in Hb will be analyzed using MMRM with the fixed effects of treatment, strata, visit, visit-by-treatment interaction and Hb level at Baseline as covariate using an unstructured covariance matrix and the Kenward-Roger method for calculating the degrees of freedom.

This MMRM analysis will implicitly impute data that was set to missing after an ICE resulting in a hypothetical strategy for handling the ICEs. Additional summary tables of change from baseline irrespective of ICEs will be created for hemoglobin with no MMRM.

Should the model fail to converge with an unstructured covariance matrix, other covariance structures will be explored (unstructured will be attempted first, followed by compound symmetry, followed by AR(1) if needed). The difference between treatment groups will be estimated, along with its 95% CI and p-value.

### **7.2.3 Transfusion avoidance (Yes/No) from Week 5 to Week 24**

Transfusion avoidance (Yes/No) from Week 5 to Week 24 (Day 29 until end of double-blind period, which is Week 24 or early withdrawal) will be tabulated by treatment group and compared between treatment groups using an exact CMH test stratified for the criterion used for randomization stratification ( $\geq 1/0$  transfusions during the 6-month period prior to randomization). The odds ratio of showing transfusion avoidance from Week 5 to Week 24 for the pegcetacoplan treatment group versus the placebo group and associated 95% CI will be provided.

The composite strategy will be used as the estimand where patients meeting any of the ICEs will be considered as non-responders (transfusion avoidance=No).

- Withdrawal from treatment or lost to follow-up before end of the double-blind period.
- Use of prohibited medications (rituximab alone or in combination, any other complement inhibitor, any other investigational drug and plasma exchange. Phlebotomy/venesection is not included) during the double-blind period.
- Transfusion from week 5 to week 24 (Day 29 until end of double-blind period).

Transfusions before Week 5 (Day 29) are not counted and not considered an ICE but patients who withdraw or use prohibited medication before Week 5 will be considered non-responders (transfusion avoidance=No).

